3.1.4 Data synthesis

In the first instance we will produce a narrative overview of both the uses of social stories in clinical practice and data on the effectiveness of those interventions. In terms of effectiveness, we suspect that there will be an insufficient number of between-group designs to conduct a meta-analysis of these data alone; there is however likely to be a larger number of single-case studies. There are a number of available effect size metrics for single-case data and methods of quantitatively synthesising these data, but there is no clear consensus about the most appropriate method for quantifying and combining the results of single-case studies (39-44). There is also debate about the appropriateness of combining data from between-group designs and single-case designs in a single meta-analysis (43). We will not, given this lack of consensus, restrict our analysis to one method. Instead, we propose to quantify and synthesise the single-case data using a small number of the more commonly used methods (e.g., percentage of non-overlapping data, R^2 change) and examine whether the results and conclusions drawn are robust to variations in these methods of calculation.

3.2 Phase One – Modeling and Refinement of Social Stories manual

Phase one relates to aims two and three of the research objectives and focuses on identifying the components of the intervention, and the underlying mechanisms by which they will influence outcomes to provide evidence that you can predict how they relate to and interact with each other:

- 2. To conduct a qualitative analysis, with user interviews and a user focus group, to gather information relating to the optimum design and use of Social Stories in children and young people with autism spectrum disorders.
- 3. To form an expert writing panel and to develop a manualised toolkit (including a training package) of appropriate Social Stories for delivery in the school setting.

This phase of development of the intervention (drawing on the literature work from the Preclinical theory phase) will use qualitative methods to take stock of current experience and elicit the views and experiences of various stakeholders, in order to ensure that our intervention can feasibly be delivered in this particular context and to ensure the intervention is acceptable to users and providers. The interviews will be focused and the analysis (using a Framework approach) will be specifically geared to address questions of the intervention design and would be conducted over a relatively short space of time.

The results of the systematic review, including the most promising Social Story themes, templates and uses, will be fed into two groups. These two main groups will work separately but will come together as mutually agreed (at least three times) to share ideas, findings, suggestions and developments. These two groups will be I – a user group and II – an expert panel.

3.2.1 User Group

The user group will comprise of:

- Ten Parents/carers
- Five teachers
- Five young people
- Five non-research clinicians

All of the user group will have previously used Social Story interventions with children or have used a Social Story intervention themselves.

Users will be drawn from at least two geographically distinct areas and will be given information about the study through local pediatricians, child psychiatrists, clinical psychologists and child mental health nurses. Should they choose families will be invited to meet a researcher for further information on the study. We will write to clinicians and teachers in the York area who may use social stories with information regarding phase 1 of the study and presentations about the research will be given to local autism support groups (such as the ASCEND group (45).

The role of the user group will be to ensure the best design and use of social stories, and the practicality and feasibility of the intervention to be delivered. We will use interviews and focus groups to gather a range of opinions and themes about:

- the helpful and unhelpful parts of the social story intervention,
- the characteristics of individuals best placed to deliver the intervention,
- determining which professional groups are best equipped to deliver and or support this package;
- mode of delivery including the role of parents or carers
- the style and content of the manual.

- the construction of the social stories (for example the ratio of directive to descriptive sentences in the story, the use of pictures etc),
- teaching in the social story theory, and dissemination,
- joining the steering group for collaboration on monitoring study progress,
- methods of dissemination of study findings for service users.

With informed consent a qualitative researcher will be present, who will transcribe the discussions and will thematically analyse key themes around potentially successful childhood outcomes.

Qualitative semi-structured interviews will be conducted using a topic guide developed to ascertain information on perceptions about feasibility and acceptability of the intervention. In addition we will gather a range of opinions and themes about the helpful and unhelpful parts of the social story intervention, the characteristics of who would be best placed to deliver the intervention, determining which professional groups are best equipped to deliver and or support this package; mode of delivery including the role of parents or carers, and the style of the manual. Where appropriate this may include information on the construction of the social stories (for example the ratio of directive to descriptive sentences in the story, the use of pictures etc), teaching in the social story theory, and dissemination.

Our group has considerable experience and expertise in this area and we would draw upon this when conducting the qualitative component of our programme of research. In addition we will carefully ask parents/carers and young people themselves which of many possible ways of conducting the qualitative feedback they would prefer and will be guided by this. In this way the user participation will be central in determining the best mechanisms for qualitative feedback.

Qualitative interviewers will have experience of working with children and young people with autism spectrum disorders. Techniques that may facilitate good feedback used in previous work will be employed. This may include using visual prompts, drawing, the Picture Exchange Communication System, using MSN and a range of other non-threatening techniques for discussion and feedback, depending on developmental stage of the child or young person.

3.2.2 Expert Group

The expert group will comprise of:

- Social Stories designer [name] (co-applicant)
- Other co-applicants with expertise in Social Stories,
- Other co-opted experts in the field of autism and the use of Social Stories,
- A PPI parent (co applicant author of a paper on the use of Social Stories in mainstream schools)
- National Autistic Society (NAS) representative
- At least 2 people who have expertise in developing and delivering training packages for parents in a child mental health setting.

The expert panel has been kept separate at the request of the PPI representatives in the research design as a mechanism for ensuring that their voices are heard in the user group and not drowned out by clinicians or academics. The important need to bring the groups together will be met by regularly mutually agreed meetings which will give equal opportunities for everyone to have their say.

The expert group will formulate a manualised approach informed by the systematic review, the expert opinions, user group feedback and the thematic analysis from the qualitative researcher. The objectives of the expert group are to:

- To balance and evaluate the existing Social Story model and write guidelines with new information arising from the systematic review and user and expert groups.
- To produce a manual on using Social Stories
- To produce a training package to train the service providers in use of the manual and provide familiarisation with the manual itself
- To focus on the design of an intervention that is fit for purpose in a mainstream school setting
- To advise about recruitment to the study

These two groups (an expert panel and a user group) working in tandem will therefore use an iterative process of feedback and redevelopment. This will lead to the generation of a list of Social Story uses that:

- 1. Have the strongest evidence base for efficacy and generalisablity
- 2. Have had positive user feedback and evaluation
- 3. Can be manualised
- 4. Are readily teachable

The focus groups will provide insight into the process of developing and using a Social Story as well as its content. This will aid us in the construction of a manualised toolkit of appropriate Social Stories for delivery in the mainstream school setting, adaptable for individual use, which we will validate in phase two. This information will be collated for the panel of experts who will formulate a manualised approach informed by the systematic review, the expert opinions, user group feedback and the thematic analysis from the qualitative researcher. This manualised approach will then be represented to the focus groups for further discussions using a SMART (Specific, Measurable, Achievable, Realistic, and Time limited) approach, for example; are the Social Stories from the manual likely to be faithful to the Social Story model? The group will include at least two people who have expertise in developing and delivering training packages for parents in a child mental health setting. In this way the manual will be complemented by a training package.

A key part of this process will be the need to balance and evaluate the existing Social Story model and rules with new information arising from the systematic review and user and expert groups. We will have full intellectual freedom to challenge and adapt any aspects of the model. In particular we are focusing on the design of an intervention that is fit for purpose in a mainstream school setting, where previously it has been extensively used in special school, home and clinic settings.

3.2.3 Manual Development and Pilot

The manual will be written by the expert group informed by the systematic review, the expert opinions and user group feedback. The user groups have already been clear about the need for;

- simplified, compact guidance on producing Social Stories,
- a clear, starting point from which to develop Social Stories once a challenging behaviour had been identified
- guidance on the use of strategies for making sense of this behaviour and how to determine the focus of the Social Story, which may be different to working on the challenging behaviour as such

- collaboration in writing Social Stories between parents and teachers,

Once initial decisions have been made regarding the refined intervention, five user/family and service provider 'dyads' as identified through the user group will be asked to 'walk through' the proposed package of care. Both users/family members and practitioners delivering the care will be interviewed (using a topic guide) to elicit their experiences and to raise any issues of concern. Practitioners applying the manual will also be asked to keep a reflective diary of the intervention process to note any issues or observations concerning the service provision. In particular they will be asked about facilitators and barriers to its delivery within existing service models; their perceptions of whether the intervention does or doesn't work well, including their understanding of why; and any experiences users have receiving the intervention which highlight where it works well and less well, including perceptions of reasons for discontinuation with the intervention by any participant. These will be analysed as qualitative documents. Any final amendments would then be made to the manualised Social Stories intervention.

The manual will be revised at all stages in the process. Throughout the intervention period, practitioners applying the manual will also be asked to keep a reflective diary of the intervention process to note any issues or observations concerning the service provision. Any final amendments would then be made to the manualised Social Stories intervention

3.2.4 Research outputs

By the end of this developmental phase (PHASE I), we will have produced a manualised intervention (including a training package to train the service providers in use of the manual and the manual itself) which will have been 'piloted' by a sample of users and their families who would be eligible to participate in the trial. Our intervention will then be amenable to evaluation in a pilot trial feasibility study.

This work will then be finalized into a manual for use in phase II. The manual content will be determined by phase one of the study but may be likely to include:

- A template element
- Guidance on Social Story development and construction
- Elements that can be tailored to any child
- Specific guidelines on Social Story elements that reduce challenging behaviour.

3.3.1 Phase Two - Exploratory Trial

Phase two involves describing the constant and variable components of the Social Stories intervention and the development of a feasible protocol for comparing the intervention to an appropriate alternative. This phase relates to aims 4, 5 and 6 of the research objectives as follows;

4. To conduct a feasibility study in the form of a randomised controlled trial comparing the manualised Social Stories intervention with an attention control (demonstrating recruitment, delivery of the intervention and successful follow up).

5. To establish the acceptability and utility of the manualised Social Stories intervention to parents and carers

6. To identify parameters, outcomes and cost effectiveness from the feasibility study in order to inform a future full scale RCT.

The validation stage of the manualised toolkit developed in phase 1 will take the form of a feasibility randomized controlled trial comparing the use of the toolkit versus an attention control I. The exact procedures will be informed by the preclinical theory phase and phase I of the study.

3.3.2 Identifying Participants

As with all local research studies we will let the local community know that they are taking place. We will give presentations about the research to local autism support groups (such as the ASCEND group; (45)). We will also provide presentations and leaflets to local autism support groups and through clinicians to parents of children with ASD attending mainstream schools. In the North Yorkshire and York PCT we have approximately 800 children with diagnoses on the autism spectrum. Given previous studies in autism in the locality and good relations with parents and parent support groups, we feel confident that will achieve our recruitment targets.

Letters will be sent to the parents of all children on the autism spectrum attending participating mainstream schools to let them know about the study and to provide a point of contact should they be interested in participating. There is in York and surrounding area a York Autism Spectrum Disorders Forum which is a multi agency multi disciplinary forum for diagnosing and discussing provision of supporting interventions for all local children on the autism spectrum. We will cross check the education list against this list to ensure that we have missed no children in participating mainstream schools with ASD.

We will use other methods of recruitment where appropriate, as advised by the service user parents on the steering group.

3.3.3 Recruitment

Interested families will be invited to meet a researcher for further information if their child has a diagnosed ASD and behavioural problems in a mainstream school. We will recruit 50 children attending mainstream schools, with autism spectrum disorders (Autism, Asperger syndrome and Atypical autism), using ICD-10 research diagnostic criteria [RDC] (46), supported by ADI-R (47) and/or ADOS (48). Other developmental disorders will not be included.

Schools will be approached to take part in the study through an existing network of clinical and educational practitioners and researchers. Co-applicant [name] has previously facilitated many research studies across the full range of schools as part of his role within the Local Authority. There are 72 primary schools in the York Local Authority and 10 secondary schools. Two of these secondary schools are designated as ASD supportive schools, although all the other schools have some young people with ASD within them. We have already had preliminary discussions with a number of secondary and primary schools that are supportive of this bid and we are confident that we can recruit 30 children within primary schools and 20 young people within secondary schools without difficulty. We anticipate that this will be in 4 secondary schools and 10 primary schools, although we will test the feasibility of this and be adaptable to recruit more or less by rolling out school involvement and leaving enough time in the study for flexibility. We will stratify school randomization to take into account numbers of ASD children, levels of ASD support, socio economic indices and Ofsted value added scores. We will ask the local multi agency autism strategy group to compare the two groups of schools generated for equivalence. Any concerns will be fed back to the steering group and the matching process will be considered as part of the feasibility work.

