Target Population: Children (aged 4-15) in mainstream school settings with a diagnosis of ASD according to ICD-10 research diagnostic criteria (WHO, 1993), ADI-R (Lord et al, 1994) and ADOS (Lord et al, 2000), who exhibit challenging behaviour in the school setting. This will be assessed using instruments informed by the systematic review (examples include the Strengths and Difficulties Questionnaire (SDQ) and the Developmental Behaviour Checklist (DBC)). We will also set a clear goal with the child, family and teacher and rate it using Likert scales before and after the study. Schools will be approached through an existing network of clinical and educational practitioners and researchers led by co applicant [name].

Intervention: A manualised toolkit of appropriate Social Stories for use with school aged children exhibiting challenging behaviour within the mainstream school setting. The toolkit and exact methodology of the feasibility study will be determined in earlier phases of the study. The comparator treatment will be an attention control.

Both arms will receive treatment as usual, for example, behavioural approaches, parenting support, systemic approaches and social skills training.

Outcomes: Primary Outcomes: utility and acceptability to parents/teachers/children of using the manualised Social Stories intervention in a mainstream school setting, as assessed by qualitative interviews and questionnaires. Secondary Outcomes: Acceptability of the research methods (e.g. randomisation procedure) to parents /carers /teachers/ children. Standard deviations of the measures used (e.g. SDQ, DBC, Likert Scales) in the two groups (Social Stories and attention control) to inform power calculation.

Economic Evaluation: The economic evaluation will take the form of within-trial costeffectiveness analysis that will determine the incremental cost per unit of effectiveness measure for Social Stories compared with an attention control in children with autism.

Sample Size: 10 parents, 5 children/young people, 5 teachers and 5 non research clinicians will be involved in the qualitative interview phase. The manualised intervention will be delivered to 25 children (and 25 children in the control group) in our feasibility study, where we will demonstrate recruitment, attrition and follow up rates, with preliminary estimates of effect size to inform sample size calculations for a full trial.

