3.3.4 Randomization

We will adopt a cluster randomization approach. This is to minimize the likelihood of participants in the different intervention groups being affected by changes in teacher or school behaviour. It also recognizes that social story expertise within a school is likely to be enhanced by sharing of skills and networking of ideas, and this design therefore more accurately reflects what would happen if social stories were used within a school in practice. We will use the qualitative interviewing within the feasibility design to explore this further, as described below.

To reduce detection bias we will first recruit the mainstream schools to be involved in the study. Then subsequently we will consent children and their families within these selected schools for involvement in the study. Only then will we randomize the schools into schools where the intervention takes place and those where it does not but where we are monitoring outcomes in the same way as in the intervention school. Participants will be randomised at whole school level, thus all children with ASD within any given school will be randomised to the same arm of the trial. This will minimize contamination as the likelihood of participants in the different intervention groups being affected by changes in teacher or school behaviour will be reduced. In order to limit detection bias, participants will be receive the Social Story intervention. The control school children will receive an equivalent amount of time reading a story of similar length and linguistic complexity a range of which will be chosen by the expert panel as an attention control. In both schools children will receive all other treatment or support as usual and we will monitor carefully what this is.

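### Stratifying about 14 schools on four factors needs at least 16 strata if they are fully crossed, and it leaves out primary/secondary

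*Protocol*

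**What the plan says.** Protocol section 3.3.3 (Recruitment) names the factors: "We will stratify school randomization to take into account numbers of ASD children, levels of ASD support, socio economic indices and Ofsted value added scores". On school numbers it says "We anticipate that this will be in 4 secondary schools and 10 primary schools", with freedom to "be adaptable to recruit more or less by rolling out school involvement". On children, the team is confident that "we can recruit 30 children within primary schools and 20 young people within secondary schools without difficulty". Primary or secondary phase is not among the four factors, although recruitment is planned by phase.

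The balance check comes after the draw: "We will ask the local multi agency autism strategy group to compare the two groups of schools generated for equivalence". Concerns then go to the steering group, and the section ends by calling the procedure matching and making it part of the feasibility work.

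Section 3.3.4 (Randomization) sets the unit: "Participants will be randomised at whole school level". It also sets the order. Schools are recruited, then children and families consent, and "Only then will we randomize the schools into schools where the intervention takes place". The Summary gives the target: "The manualised intervention will be delivered to 25 children (and 25 children in the control group").

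The protocol does not say how many levels each factor has, whether the factors are crossed, or what block size or algorithm is used.

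**The concern.** Stratified blocks balance the arms only when the strata hold enough units to fill the blocks. With more strata than schools, many strata hold one school, and that school is in effect allocated by a coin toss. Because whole schools are randomised, an uneven draw moves several children at once.

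The omitted factor matters as well. Phase fixes age range and setting, and 4 schools are expected to carry 20 of the 50 children (40%). Section 3.3.9 keeps the age range wide in order to explore acceptability in primary and secondary schools, and section 3.3.14 plans to examine age effects. If most secondaries fall in one arm, the arm-level standard deviations, attrition and acceptability findings meant to inform a full trial are mixed up with school phase.

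The later check by the local group can notice an imbalance but cannot prevent one. It has no criterion, and beyond referral to the steering group no consequence is stated.

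**Working it through.** **Inputs from the protocol.** 10 primary and 4 secondary schools; 30 primary and 20 secondary children; four factors; 25 children planned per arm.

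**Assumptions, not in the protocol.** Each school is at the mean size for its phase, 30/10 = 3 or 20/4 = 5 children. Factors are fully crossed with permuted blocks inside strata, and schools are spread evenly over independent factors. Departures are shown below.

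**The plan's own figures.** 10×3 + 4×5 = 50. An arm with p primaries and s secondaries has 3p + 5s children. The only solution for 25 is p = 5, s = 2, so the target is attainable at mean sizes. The recruitment-rate precision in section 3.3.10 also reproduces, 1.96×√(0.85×0.15/50) = 0.099, and is untouched by this point.

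**Number of strata.** Two levels each: 2^4 = 16. One factor at three levels: 3×2^3 = 24. All at three levels: 3^4 = 81. The smallest full crossing already exceeds 14.

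**How thin the 16 strata are.** Expected occupied strata: 16×(1 − (15/16)^14) = 9.5. Expected strata with one school: 14×(15/16)^13 = 6.1. Expected strata with an odd number: 8×(1 − (7/8)^14) = 6.8.

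**Reference schemes, exact.**
- Independent coin tosses: variance of children in one arm = (10×9 + 4×25)/4 = 47.5, SD 6.9. P(25/25) = 252×6/16384 = 9.2%. P(secondaries not 2:2) = 1 − 6/16 = 62.5%.
- Plain 7:7 draw of schools: children = 21 + 2x for x secondaries. P(25/25) = P(2:2) = 6×252/3432 = 44.1%; P(3:1) = 49.0%; P(4:0) = 7.0%. The range is 21 to 29 children, so 20:30 cannot occur. SD 1.75.

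**Stratified schemes, simulated (30,000–40,000 draws each).**

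| Scheme | Exact 25/25 | 20:30 or worse | SD of children in one arm | Share of coin-toss variance | Secondaries not 2:2 |
|---|---|---|---|---|---|
| Coin toss | 9% | 55% | 6.9 | 100% | 62.5% |
| 16 strata, blocks of 2 | 13% | 41% | 5.0 | 52% | 59% |
| 16 strata, blocks of 2, size factor identical to phase | 19% | 43% | 5.1 | 54% | 53% |
| 16 strata, blocks of 2, strongly correlated factors | 17% | 34% | 4.3 | 38% | 58% |
| 16 strata, blocks of 4 | 11% | 49% | 6.0 | 76% | 61% |
| 24 strata, blocks of 2 | 12% | 45% | 5.5 | 63% | 60% |
| 81 strata, blocks of 2 | 10% | 52% | 6.4 | 86% | 61% |
| Plain 7:7 draw | 44% | 0% | 1.75 | 6% | 56% |

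The variance share is SD²/47.5, for example 4.97²/47.5 = 52%. Repeat runs of the two-level, blocks-of-2 scheme with independent factors or with size tied to phase stayed within 13–19%, 41–44% and 53–60% for the three percentages.

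**Unequal school sizes.** Letting sizes vary within phase, 16 strata give exact 25/25 in 7% and 20:30 or worse in 42%. The plain 7:7 draw gives 12% and 18%, so its advantage shrinks but remains.

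**The case against.** The protocol does not fix a crossed, blocked scheme. It says the randomisation will take the four features into account and then speaks of matching. Two of the features, socio-economic indices and value-added scores, are naturally continuous and need not be crossed. Matching, minimisation or constrained randomisation is not ruled out, and levels and algorithm are commonly left to a randomisation plan or SAP that is not shown. This stands: every percentage above is conditional, and the missing detail is not itself a fault. What remains is that stratification is the stated method, the four factors are too many for the schools if crossed, and phase is not named.

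A reader might infer that the allocation is close to coin-tossing throughout. The figures do not support that. Two levels per factor remove about half of the coin-toss variance in children per arm and lower the chance of 20:30 or worse from 55% to about 41–44%. The description fits the primary/secondary split, and arm size only with finer levels, which the protocol does not state.

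A reader might also blame the four-factor scheme for uneven secondary splits. A plain 7:7 draw gives nearly the same rate (56%), so the cause is the omission of phase. Number of ASD children and level of ASD support partly stand in for phase, but making the size factor identical to phase still leaves 53% not split 2:2.

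Finally, 25/25 is a planning count, school numbers are flexible, and this is a feasibility study with acceptability outcomes that is declared not powered for differences. This limits the harm without removing it.

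**Conclusion.** The point holds in a limited form. Full crossing of the four named factors needs at least 16 strata for about 14 schools, and school phase is left out although 4 schools are expected to hold 40% of the children. With two levels per factor, blocks of 2 and mean school sizes, the scheme balances arm size worse than a plain 7:7 draw: exact 25/25 in about 13–19% against 44%, and 20:30 or worse in about 41–44% against 0%. Strong correlation between factors lowers the second figure to 34%; larger blocks or finer levels raise it. Large imbalance in children is therefore a substantial risk, but in this scenario it is not the more likely outcome. An uneven secondary split is more likely than not (about 53–60%), as it would be under any scheme that ignores phase. The consequence is weaker comparability and weaker arm-level estimates for planning the full trial.

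**What to change.** Replace the four-factor stratification in section 3.3.3 with covariate-constrained randomisation, which is usable because section 3.3.4 has schools recruited and children consented before allocation. Require near-equal numbers of schools, of primaries and secondaries, and of consented children per arm, and put ASD support, socio-economic index and value-added score in the balance score. If schools join in batches, use minimisation with a random element on the same variables. Have the local autism strategy group agree the balance criteria before the draw, in place of judging equivalence after it, and use one name for the method throughout.

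Holding 5 primaries and 2 secondaries per arm gives exactly 25/25 at mean sizes and still leaves 252×6 = 1,512 possible allocations. With unequal sizes, that restriction alone puts 20–30 children in each arm in about 94% of draws; adding balance on consented children gives 23–27 in more than 99%. Those simulations balanced only phase and children, so including the other three factors will give back some of this.

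The cost is a short randomisation script, a sentence in the protocol, slightly more set-up, and waiting until a batch of schools is ready.
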